such as bilateral thigh cuff inflation to suprasystolic blood pressure and their simultaneous release, lower body negative pressure, and the cold pressor stimulus (placing a hand in ice water). These can be uncomfortable for participants. More recently, squat-stand manoeuvres (SSMs) have also been shown to produce large changes in BP and thus CBFv [Claassen et al 2009a, Smirl et al 2015, Barnes et al 2017]. Squatting induces a rapid but transient rise in BP with its peak after approximately 2-3 seconds (s). This increase in BP has been attributed to a sudden increase in cardiac output from increased venous return from the lower limbs. The subsequent reduction in BP on standing up has been attributed to a combination of reduction in peripheral vascular resistance and a reduction in cardiac output due to rapid return of central blood volume to the lower limbs [Smirl et al 2015]. SSMs can be more comfortable for participants and are arguably more representative of physiological BP challenges in daily life, e.g. bending down to pick something up from the floor and standing up after tying a shoelace, than those other BP challenges detailed above. When SSMs are performed repeatedly, large and periodic changes in BP and CBFv are created. SSMs have been shown to be safe and well tolerated in various populations including heart transplant recipients [Smirl et al 2014], young and old healthy controls [Oudegeest-Sander et al 2014, Barnes et al 2017], and patients with Alzheimer's dementia [Claassen JA et al 2009b]. It has recently been shown that reliable CA data can be obtained from as few as three SSMs [Barnes et al 2018].

The proposed study will investigate and compare the beat-to-beat CBFv changes observed during performance of a SSM protocol in 20 participants with acute (within 7 days) TIA and 20 HC. The proposed study will also investigate whether performance of a SSM is associated with differences in other beat-to-beat cerebral haemodynamic parameters, specifically autoregulation index (ARI), between participants with acute (within 7 days) TIA and 20 HC. In doing so, it is hoped that we will be able to establish if CA is impaired in patients with TIA.

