7.2 Inclusion Criteria

HEALTHY CONTROLS:

- Willing to participate
- Capacity to consent to the study
- Aged over 18 years
- Able (in the Investigator's opinion) and willing to comply with all study requirements
- Good understanding of written and verbal English

TIA PATIENTS:

- Willing to participate
- Capacity to consent to the study
- Aged over 18 years
- Able (in the Investigator's opinion) and willing to comply with all study requirements
- A diagnosis of acute (≤ 7 days) TIA, made by a specialist in the TIA clinic at University Hospitals of Leicester NHS Trust that fulfils the 2009 American Heart Association definition of TIA
- Good understanding of written and verbal English

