8. STUDY PROCEDURES

8.1 Screening and Eligibility Assessment

Patients attending the specialist TIA clinic at University Hospitals of Leicester NHS Trust will be eligible for recruitment into the study.

Medical records will be reviewed by the direct care team to ensure participants meet the inclusion and exclusion criteria. Eligibility screening will only be undertaken by the direct clinical care team for potential participants.

Participants will be approached at their clinical consultation in the specialist TIA clinic by consultants, registrars or specialist nurses to determine study interest prior to referral to the researcher and provision of study specific information. A poster advertising the study will be displayed in the TIA clinic waiting room. Both participants with TIA, and healthy controls (those without a diagnosis of TIA) will be recruited from the clinic. Healthy spouses, friends or partners of patients with TIA will be asked if they would like to participate in the study as a healthy control subject.

TIA participants will be given a minimum of 1 hour, and a maximum of 48 hours to decide whether or not to take part in the study, but must undertake the study assessment within 7 days of their TIA.

Healthy control participants will be given a minimum of 1 hour, and a maximum of 7 days to decide whether or not to take part study. There is no time restriction on when they undertake the study assessment.

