8.4 Collection of demographic data

To avoid repetition and undue burden to participants, consent will be obtained from participants to record the following data from their TIA clinic letter as detailed below:

- Date of birth
- Gender
- Height
- Weight and BMI
- Past Medical History
- Current Medications
- GP name and address
- Smoking status
- Capillary blood glucose
- Carotid ultrasound result
- Type and result of brain imaging

Healthy controls will be asked the above information directly, although will be unable to provide capillary blood glucose, carotid ultrasound or brain imaging results.

- Participants will be asked to detail their ethnicity according to the 18 standardised ethnic categories outlined in the 2011 Office of National Statistics census (Appendix A)
- Handedness will be determined for all participants using the Edinburgh Handedness Inventory [Oldfield 1971] (Appendix B)

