11. STATISTICS

11.1 Statistical analysis

The null hypotheses being tested are:

- cerebral haemodynamic parameters, including CBFv and ARI, do not differ between baseline recordings and during performance of squat-stand manoeuvres
- cerebral haemodynamic parameters, including CBFv and ARI, do not differ between TIA patients and HC

All data will be tested for normality prior to statistical testing using Shapiro-Wilks. Categorical data will be reported as absolute number and percentages. Continuous data will be plotted and assessed for normality; normally distributed continuous variables will be described as mean (SD) and continuous variables with skewness as median (IQR). Statistical testing for differences between HC and TIA groups will be by two-way ANOVA for continuous, parametric data, Friedman 2 way analysis of variance for continuous, non-parametric data, and Chi-Square for nominal data.

Data will be recorded in Microsoft Excel. Statistical analyses will be performed using the latest versions of SPSS for Windows or Statistica, and graphs will be produced using the latest version of Statistica.

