11.2 Sample size calculation

A formal sample size calculation was not possible for this study therefore a realistic number of participants has been selected based on previous experience of similar research studies by [name], [name] and [name].

Brodie FG et al reported in 2009 that a sample of 11 patients per group will allow the detection of a difference in ARI of 2 units between groups, with 80% power at the 5% significance level.

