15. DATA HANDLING AND RECORD KEEPING

15.1 Data Extraction

As supportive evidence of the diagnosis of TIA in TIA participants, results and significant findings from Computerised Tomography (CT) head/Brain Magnetic Resonance Imaging (MRI) and Carotid Ultrasound, if undertaken, will be recorded on the CRF.

Other information which will be extracted from the medical notes of TIA participants and recorded on the CRF include smoking status, capillary blood glucose, medications, past medical history, height, weight and BMI.

The medical notes of healthy control participants will not be reviewed, and participants will instead be asked their smoking status, medications, past medical history, height and weight directly. Answers to these questions will be recorded on the CRF.

Data regarding participants' age, date of birth, ethnicity and handedness will also be recorded onto the CRF. All other parameters, including CBFv, squat angle, heart rate (HR), BP, and ETCO₂, will be recorded onto a computer system (PHYSIDAS), providing data for subsequent analyses.

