16. STUDY GOVERNANCE

The trial management group, which consists of the CI, co-investigators, and other research staff, will meet monthly to monitor study progress, and recruitment targets. As this is a prospective case control study, and not a therapeutic study, a data safety monitoring committee is not required.

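### The TIA versus control comparison of CBFv and ARI is neither matched on nor adjusted for age and sex, although both are recorded for every participant

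*Combined protocol and SAP*

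**What the plan says.** Section 11.1 states two null hypotheses. One is that CBFv, ARI and other parameters do not change between baseline and the squat-stand manoeuvre. The other is that they do not differ between TIA patients and healthy controls. For the second it says: "Statistical testing for differences between HC and TIA groups will be by two-way ANOVA for continuous, parametric data, Friedman 2 way analysis" of variance for non-parametric data, and chi-square for nominal data. The two ANOVA factors are not named, and no covariate, ANCOVA or regression model appears anywhere in the document.

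The design is a single-centre case-control study with 20 participants per group (section 2). The only age criterion, identical for both groups in section 7.2, is "Aged over 18 years". On the source of controls, section 8.1 says: "Healthy spouses, friends or partners of patients with TIA will be asked if they would like to participate in the study". No section sets matching, frequency matching or a balance target.

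The data needed for adjustment are planned. Section 8.4 takes date of birth and gender from the clinic letter for TIA patients and adds: "Healthy controls will be asked the above information directly". Section 15.1 confirms that "age, date of birth, ethnicity and handedness will also be recorded onto the CRF"; its own list leaves out gender, but section 8.4 covers it.

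**The concern.** Section 4 gives the comparison its purpose: "it is hoped that we will be able to establish if CA is impaired in patients with TIA". In a non-randomised comparison, that reading requires the groups to be alike in whatever else affects autoregulation, or the analysis to allow for the differences. The plan arranges neither for age or sex.

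If TIA patients and controls differ in age or sex, and ARI or CBFv depends on that variable, the unadjusted group difference is the TIA effect plus a demographic bias. The bias could create an apparent impairment or hide a real one. Baseline summaries would reveal an imbalance but not remove its effect. Choosing covariates after seeing it would leave the result open to the charge of selection.

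Exposure differs by outcome. ARI and absolute CBFv are the most exposed. For percentage change in CBFv, proportional differences in resting velocity cancel, so only age or sex effects on the response itself matter. The count outcomes in section 6.2 are unaffected.

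**Working it through.** **1. The plan's own figure.** Section 11.2 says there is no formal sample size calculation, but cites a study in which "a sample of 11 patients per group will allow the detection of a difference in ARI of 2 units between groups". The power quoted for that figure is 80% and the significance level 5%. The section gives no SD and does not say whether the test is one- or two-sided. The 11 per group therefore cannot be reproduced independently, but it can be solved for the SD. For a two-sided two-sample t-test with 20 df, 80% power needs a standardised difference d = 1.256, so SD = 2 / 1.256 = 1.59 ARI units. Read as one-sided, the implied SD is 1.82.

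**2. False-positive rate under confounding.** The following inputs are assumptions, because the documents supply none.

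- Bias in SD units: b = (sex imbalance × sex effect) + (age gap / 10) × (effect per decade).
- Noncentrality with 20 per group: b / √(2/20) = 3.162 × b.
- Two-sided 5% t-test, 38 df, no TIA effect.

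| Assumed scenario | b (SD) | Rejection rate |
|---|---|---|
| No imbalance | 0 | 5.0% |
| Sex: 24 points × 0.5 SD | 0.12 | 6.6% |
| Sex: 30 points × 0.8 SD | 0.24 | 11.5% |
| Age: 10 years × 0.2 SD per decade | 0.20 | 9.5% |
| Age: 15 years × 0.3 SD per decade | 0.45 | 28.4% |
| Both: 0.24 × 0.5 + 1.0 × 0.2 | 0.32 | 16.7% |

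At the low end (12 points × 0.3 SD, or 5 years × 0.1 SD per decade), b is 0.04 to 0.05 SD and the rate is barely above 5%. The combined scenario amounts to 0.32 × 1.59 = 0.51 ARI units. A larger sex imbalance can do the same without any age gap: 40 points × 0.8 SD also gives 0.32 SD and 16.7%.

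**3. Does adjustment remove it?** The combined scenario was simulated with 10,000 runs, within-group age SD 12 years, residual SD 1, and male share 65% versus 41%. The unadjusted test rejects in 15.7% of runs and the age- and sex-adjusted test in 5.0%. The variance of the group effect is inflated 1.33-fold. The unadjusted rate is slightly below 16.7% because here the residual SD, not the total SD, is set to 1. With no imbalance the rates are 4.8% and 4.9%, and the inflation is 1.06.

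**4. Price in power for 2 ARI units.** Unadjusted, 20 per group, SD 1.59: noncentrality 1.256 × 3.162 = 3.97, power 97.2%. Adjusted: divide the noncentrality by √(VIF × (1 − R²)) and use 36 df, where VIF is the variance inflation and R² the share of outcome variance explained by age and sex. For example, VIF 1.25 with R² = 0 gives 3.97 / 1.118 = 3.55 and 93.3%.

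| VIF | R² = 0 | R² = 0.20 |
|---|---|---|
| 1.1 | 95.8% | 98.5% |
| 1.25 | 93.3% | 97.2% |
| 1.5 | 88.4% | 94.1% |

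With the one-sided reading (SD 1.82), unadjusted power is about 92%, and the R² = 0 column becomes about 90%, 86% and 79%.

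These calculations treat the group effect as a single two-sample test. They approximate the between-group part of a two-way ANOVA whose factors the plan does not name.

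**The case against.** The strongest reply is that both links needed for bias are assumed. The documents do not say that the groups will differ in age or sex, nor that ARI or CBFv depends on either; section 4 gives one normal ARI range with no age or sex strata. This stands. It limits what can be said about size and direction, but not the finding that the plan has no safeguard.

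Second, spouses and partners may be close to patients in age, which would keep the inflation at the low end. That is fair as mitigation. However, section 8.1 is an invitation that also covers friends, and the analysis does not pair controls with patients. Opposite-sex couples could widen a sex imbalance if the patients are mostly of one sex.

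Third, the outcomes in section 6.2 are feasibility counts, and section 4 only hopes to establish impairment. This lowers the stakes, but section 11.1 still states a formal TIA versus control null hypothesis and section 11.3 sets a 5% level.

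Fourth, the unnamed second ANOVA factor might be age or sex. The two null hypotheses point instead to group and recording condition. If a demographic factor was meant, the plan needs to say so.

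Finally, age and sex are not the only possible confounders. Section 8.4 also records smoking, medication and medical history, and section 9.2 has TIA patients receiving blood-pressure-lowering therapy. This stands too: the simulated return to 5% assumes that age and sex are the only confounders and act linearly. Adjustment for them narrows the problem without closing it.

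**Conclusion.** The concern holds. It is clear from the text that the plan neither balances the groups on age and sex nor adjusts for them. Whether this will distort the result, by how much and in which direction, cannot be known from the documents. Over the ranges assumed here, a nominal 5% test rejects in 5% to 28% of studies with no TIA effect, and about 17% in the combined mid-range scenario. With close balance there is no inflation. The power figures rest on an SD inferred from the cited sample size under a two-sided t-test. This is an improvement that should be made: the consequence is uncertain, but the remedy is cheap and must be fixed before the data are seen.

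**What to change.** In section 11.1, pre-specify age (continuous) and sex as covariates in the TIA versus control comparison of CBFv and ARI. Use ANCOVA, or a group-by-condition model with the same covariates, and name its factors. Where normality fails, use a transformation or the same adjusted model on ranks; Friedman's test takes no covariates. Report the adjusted difference with its 95% CI as the main between-group result and the unadjusted difference as secondary. Tabulate age and sex by group, and state that other confounders may remain.

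Optionally, review the age and sex balance of controls as recruitment proceeds. Under section 16 the trial management group already "will meet monthly to monitor study progress, and recruitment targets". Frequency matching on age band and sex would be an alternative.

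The cost is a change of wording, 2 of 38 degrees of freedom, and some precision if age or sex is correlated with group. Two covariates remain affordable at 40 participants. Steering control recruitment towards balance might slow it slightly.

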2. SYNOPSIS

Study Title	THE ASSESSMENT OF CEREBRAL HAEMODYNAMICS IN PATIENTS WITH TRANSIENT ISCHAEMIC ATTACK: A TRANSCRANIAL DOPPLER STUDY
Internal ref. no.	UNOLE 0694
Trial Design	Single-centre, prospective, case control study
Trial Participants	Participants with Transient Ischaemic Attack (TIA) and healthy adults (HC)
Planned Sample Size	40 participants in total; 20 participants with TIA and 20 HC
Follow-up duration	N/A
Planned Trial Period	6 months
Primary Objective	To determine the beat-to-beat cerebral blood flow velocity (CBFv) of both TIA and HC subjects during performance of a squat-stand manoeuvre
Secondary Objective	To determine other beat-to-beat cerebral haemodynamic parameters, specifically autoregulation index (ARI), of both TIA and HC subjects during performance of a squat-stand manoeuvre
Outcome Measures	
This is not an intervention study, and therefore it would not be appropriate to assess classical primary and secondary outcome measures such as death and disability for this study. However, we intend to evaluate the following relevant outcomes:
 
 1. The number of participants successfully recruited 2. The number of recruited participants able to comply with the full measurement protocol. 3. The number of measurements rejected because of aspects related to data quality during the analysis protocol, with recorded reasons. 4. Overall, the number of recruited subjects in whom values for the following parameters can be derived: 
 • % change of cerebral blood flow velocity (CBFv) at baseline in response to performance of a squat-stand manoeuvre • Autoregulation index

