8.5 TCD Assessment

For all subjects, all assessments will be undertaken in a dedicated cardiovascular research laboratory at Leicester Royal Infirmary (LRI), which is at a controlled temperature (20-24°C) and is free from distraction. Participants will be asked to refrain from heavy meals, strenuous exercise, alcohol, smoking and caffeine if possible for four hours prior to attending the research laboratory. Baseline brachial casual BP will be measured using a validated UA767 BP monitor. Beat-to-beat non-invasive BP will be recorded continuously using the Finometer cuff device (Finapres Medical Systems; Amsterdam, The Netherlands) attached to the middle finger of the right hand which will be supported in an arm sling. R-R interval will be recorded using a 3-lead electrocardiogram (ECG). Respiratory rate will be recorded, and end-tidal partial pressure of carbon dioxide (EtCO₂) will be monitored using small nasal cannulae placed at the base of the nose (Salter Labs, ref 4000) attached to a capnograph (Capnocheck Plus) to monitor the breathing. A tilt sensor will be attached to the thigh of the participant's right leg by means of a Velcro strap to measure the efficiency and angle of the squatting motion. Simultaneous bilateral insonation of the middle cerebral arteries (MCAs) will be performed using TCD with 2MHz probe using a DWL Doppler box, with the subject either sitting or lying supine on a couch (in the case of difficult to insonate windows). The vessels will be located via the temporal bone window, and identified as the MCAs by their waveform, depth, velocities, and direction of flow. All parameters will be simultaneously recorded onto a computer software system (PHYSIDAS), providing data for subsequent off-line analysis. A head frame will be used to secure the ultrasound probes in position and to minimise their movement. Once satisfactory signals have been obtained, four recordings will be made:

- 1) A 5 minute baseline recording during which the participant sits quietly with their eyes open
- 2) A 6 minute recording during which the participant sits for 1 minute before standing and remaining standing quietly with their eyes open for 5 minutes

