11.3 The Level of Statistical Significance

Statistical significance will be set at $p < 0.05$

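### Section 11.1 names two-way ANOVA without saying that recordings are repeated within participants; run literally on all values, it would inflate TIA vs HC false positives and weaken the baseline vs squat comparison

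*Combined protocol and SAP*

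**What the plan says.** Section 11.1 sets out two null hypotheses. The first is that haemodynamic parameters, CBFv and ARI among them, "do not differ between baseline recordings and during performance of squat-stand manoeuvres". The second is that they do not differ between TIA patients and healthy controls (HC).

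The test is then named in one sentence: "Statistical testing for differences between HC and TIA groups will be by two-way ANOVA for continuous, parametric data". The same sentence gives Friedman's test for non-parametric data and chi-square for nominal data. Nothing in the section identifies the two factors, a participant term, the error term or an interaction. The sentence is about HC vs TIA differences, and no test is expressly assigned to the first hypothesis.

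Section 8.5 describes the data. Both MCAs are insonated simultaneously, and "Once satisfactory signals have been obtained, four recordings will be made", although only three are listed: seated baseline, sit-to-stand, and squat-stand. Sections 6.2 and 2 list a percentage change in CBFv and the ARI among the parameters to be derived. No section says how recordings or sides are combined before testing. The Synopsis gives the size as "40 participants in total; 20 participants with TIA and 20 HC".

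**The concern.** A two-way ANOVA needs a second factor besides group. The only evident candidates in the protocol are recording and side, and both vary within a person. A two-way ANOVA with no participant term treats every value as if it came from a different person and uses one pooled error variance for every test.

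That variance is wrong in opposite directions. Group means averaged over correlated recordings vary more than the model believes, so the TIA vs HC test rejects too often. Baseline-to-squat differences vary less than the model believes, because stable differences between people cancel, so that test rejects too seldom. The group-by-recording interaction suffers in the same way. It matters because Section 4 says the study will compare CBFv changes during the manoeuvre between the groups, and that contrast is the interaction. With 40 participants, the choice of error term could by itself change a conclusion.

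**Working it through.** **The plan's own figure.** Section 11.2 states that "A formal sample size calculation was not possible for this study" and then cites an earlier reliability study, in which "a sample of 11 patients per group will allow the detection of a difference in ARI of 2 units between groups"; the power quoted for that figure is 80%, at a 5% level. No SD is given, so 11 cannot be reproduced directly. For a two-sided comparison of two means, the SD it implies is 2 × √(11/2) / (1.960 + 0.842) = 4.690 / 2.802 = 1.67 ARI units (1.59 with the t distribution). This says nothing about within-person correlation, so it does not settle the present point.

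**Inputs from the documents.** n = 20 per group (Synopsis); significance level 0.05 (Section 11.3), taken as two-sided; baseline and squat-stand measured in the same people (Sections 8.5 and 11.1).

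**Assumptions.** k = 2 values per person; equal variances; common within-person correlation ρ of 0.3, 0.5 or 0.7 (the documents give none); normal data; values in SD units.

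**Formulas.** The ordinary ANOVA's pooled within-cell variance estimates the total variance, on 2k(n − 1) = 2 × 2 × 19 = 76 degrees of freedom, so the critical value is 1.992.

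- Group: true variance of the difference ÷ variance the model assumes = 1 + (k − 1)ρ.
- Recording and interaction: the same ratio = 1 − ρ.

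**Normal approximation to the actual size.**

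- Group: 2P(Z > 1.992/√(1 + ρ)). The arguments are 1.747, 1.626 and 1.528, giving 0.081, 0.104 and 0.127.
- Recording: 2P(Z > 1.992/√(1 − ρ)). The arguments are 2.381, 2.817 and 3.636, giving 0.017, 0.005 and 0.0003.

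**Simulation** (40,000 data sets per setting, no true effect, nominal 0.05):

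| Test, ordinary two-way ANOVA, k = 2 | ρ = 0 | 0.3 | 0.5 | 0.7 |
|---|---|---|---|---|
| TIA vs HC | 0.050 | 0.084 | 0.107 | 0.132 |
| Baseline vs squat | 0.050 | 0.021 | 0.006 | 0.001 |
| Group by recording | 0.050 | 0.020 | 0.007 | 0.001 |

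The mixed (split-plot) ANOVA on the same data held between 0.048 and 0.052 for all three tests.

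**Power for a 0.4 SD baseline-to-squat shift (illustrative).** With the within-person error term, the standard error is √(2(1 − ρ)/40) = 0.187, 0.158 and 0.122. The non-centrality is 0.4 divided by this, or 2.14, 2.53 and 3.27 on 38 degrees of freedom, giving power of 55%, 69% and 89%. The ordinary ANOVA gives 41%, 39% and 37% by simulation. For a 0.5 SD shift the figures are 74%, 87% and 98% against 62%, 63% and 67%.

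**Sensitivity to k.** If three equally correlated values per person entered the model, the group test's size would be 0.119, 0.162 and 0.207; with four (two recordings by two sides), 0.152, 0.215 and 0.265. Nothing in the documents says that the sit-to-stand recording, or both sides, would enter the same ANOVA, so k = 2 is the case to rely on.

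**The case against.** The strongest reply is that the plan is under-specified rather than wrong. A two-way ANOVA with one repeated factor is still a two-way ANOVA, and pairing it with Friedman, a related-samples procedure, suggests that repeated measurement was in mind. A reader might infer that the sponsor has chosen an independent-observations model and that the TIA vs HC p-value is therefore anti-conservative. The documents do not support that: the error term is not stated, so the consequence is conditional on how the analysis is run.

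Three further limits stand.

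- The percentage change in CBFv gives one value per participant if the two sides are averaged, and ARI could be compared within a single recording. A group comparison on one value per person has no inflation.
- A reader might infer that the first hypothesis cannot be tested parametrically under this plan. The text supports only that no test is expressly assigned to it. Applying the named ANOVA to it is an inference, so the power loss is conditional too.
- TIA vs HC is not designated as the primary test. Section 5 speaks of determining CBFv and ARI in both groups, and the outcomes in Section 6.2 are counts.

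The appeal to Friedman does not rescue the sentence. Friedman's test cannot compare two independent groups, yet it is assigned to exactly that. The wording does not separate between-person from within-person comparisons, so it cannot be relied on to imply the right error term. Nor does the percentage-change reading settle the matter: no rule for averaging sides is given, ARI is not defined as a change score, and a one-value analysis leaves the two-way ANOVA without an evident second factor.

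**Conclusion.** The concern holds in conditional form. Section 11.1 does not specify the within-participant structure, and the test it names, taken literally and applied to all values, would use the wrong error variance. The directions of error hold for any positive within-person correlation, which is to be expected for repeated measurements made in one visit.

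The sizes rest on a correlation the documents do not give and on compound symmetry, including equal variance at rest and during squatting. Under those assumptions the false-positive rate for TIA vs HC is roughly 1.7 to 2.6 times nominal (0.084/0.05 to 0.132/0.05). The within-person tests lose a modest amount of power at ρ = 0.3 and more than half of it at ρ = 0.7 (37% against 89%).

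**What to change.** In Section 11.1, replace two-way ANOVA with a mixed (split-plot) ANOVA or the equivalent linear mixed model, specifying:

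- group as a between-participant factor;
- recording as a within-participant factor, and side likewise if both MCAs are analysed rather than averaged, with the choice stated;
- the group-by-recording interaction;
- a participant random effect.

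State that this one model tests both null hypotheses and that the participant is the unit of analysis. Say which recordings enter it, and reconcile the count of four in Section 8.5 with the three listed. Reword the Friedman clause at the same time so that it is not assigned to the TIA vs HC comparison; a rank-sum test on one value per participant would be one alternative.

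Either form of the model meets the point. Choosing the linear mixed model in order to keep participants with one unusable recording is a separate missing-data decision, to be squared with Section 11.4. The cost is protocol wording: no new data are needed, and SPSS, already named in Section 11.1, can fit the model.
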